6 DETERMINATION OF SAMPLE SIZE

Due to the exploratory nature of this study, the sample size is not calculated based on statistical significance on any parameters. However, a sample size of 30 patients per group is considered to be sufficient to detect marked differences in the overall safety profile between treatments with a pre-specified safety monitoring plan. Furthermore, this sample size provides estimates of treatment differences in some clinical efficacy endpoints and the levels of some biomarkers such as CRP, for use in planning future studies. Therefore, approximately 30 patients will be enrolled for each group (total 60) in this study.

7 RANDOMIZATION

Patients will be randomized to one of the 2 treatment groups: SIR1-365 100 mg or placebo at a 1:1 ratio. Randomization will be stratified according to age group (2 levels: < 60 or \geq 60 years), Dexamethasone use (2 levels: Yes or No), and Remdesivir use (2 levels: Yes or No).

Randomization will be controlled by a web-based Randomization and Trial Supply Management (RTSM) system.

8 GENERAL ANALYSIS CONSIDERATIONS

The statistical analyses will be reported using summary tables, listings, and figures (TLFs). The International Council for Harmonisation (ICH) numbering convention will be used for all TLFs.

Unless otherwise noted, all statistical testing will be 2-sided and will be performed at the 0.05 significance level. Tests will be declared statistically significant if the calculated P-value is <0.05 .

Continuous variables will be summarized by presenting the number of observations, mean, standard deviation, median, minimum, and maximum. Other summaries (eg, 95% confidence interval [CI]) may be used as appropriate.

Categorical variables will be summarized by presenting counts and percentages of patients in corresponding categories. All possible categories as defined in the CRF should be populated, even

if they have zero counts. Percentages for missing values are omitted and do not account for the percent calculation of other categories. Percentages are based on the total category count excluding the missing category if not otherwise mentioned. In certain tables (eg, AEs), the total number of patients in the analysis set is used as denominator. Footnotes in the table will specify the percent basis in those cases.

All summary tables will be presented by treatment group and a total column (except efficacy tables). Baseline summaries will also include a total summary column.

Individual patient data obtained from the eCRFs, external vendors (eg, laboratory data, ECG data), PK data, and any derived data will be presented by patient in data listings.

The analyses described in this plan are considered a priori, in that they have been defined before breaking the blind.

Any analyses performed after breaking the blind which are not specified in this analysis plan (or subsequent version prior to unblinding) will be considered post hoc and exploratory. Post hoc analyses will be labeled as such on the output and identified in the CSR.

All analyses and tabulations will be performed using SAS software Version 9.4 or higher. TLFs will be presented in rich text format (RTF). Additionally, collated portable document format (PDF) of all tables, listings and figures will be provided. Upon completion, all SAS programs and outputs will be validated by an independent programmer. In addition, all program output will undergo a senior level statistical review. The validation process will be used to confirm that statistically valid methods have been implemented and that all data manipulations and calculations are accurate. Checks will be made to ensure accuracy, consistency with this plan, consistency within tables, and consistency between tables and corresponding data listings. Upon completion of validation and quality review procedures, all documentation will be collected and filed by the project statistician or designee.

8.1 Conventions

Derived data where it is known in advance the result will be an integer for example day, month, and year will be presented with zero decimal places.

The precision of original measurements will be maintained in summaries, when possible. Means, medians, and percentiles will be displayed to one more decimal place than the data, dispersion statistics (eg, standard deviation) will have 2 more decimal places, and the minimum and maximum will be displayed to the same number of decimal places as reported in the raw data. The 95% CI will be presented to 2 decimal places and P-values will be presented to 4 decimal places. P-values less than 0.0001 will be presented as <0.0001. Percentages will be displayed with one decimal place.

In the case where a continuous variable is recorded as “> x”, “≥ x”, “< x” or “≤ x”, a value of x will be taken for analysis purposes.

8.2 Standard Calculations

Variables requiring calculations will be derived using the following formulas:

- Baseline: A Baseline value, unless specified otherwise, is the last non-missing value recorded prior to the first dose of study drug.
- Study day: For a given date, study day will be calculated as the number of days from the day of first dosing of study drug, labeled day 1, therefore:

Study day = date of event/measurement - date of first dose of study drug + 1, for events/measurements on or after first dose

Study day = date of event/measurement - date of first dose of study drug, for events/measurements before first dose

- Durations (days): Durations, expressed in days, will be calculated as follows:

Duration in days = (Stop date/time of event – Start date/time of event)/(3660x24)

If the stop or start time is missing, only the date information will be used as follows:

Duration in days = Stop date of event – Start date of event + 1

- Height: Height entries made in inches are converted to centimeters using the following formula:

Height (cm) = Height (in) × 2.54

- Weight: Weight entries made in pounds are converted to kilograms using the following formula:

Weight (kg) = Weight (lb)/2.2046

- Body Mass Index (BMI): BMI is calculated using height and weight and is calculated using the following formula:

BMI (kg/m²) = Weight (kg) / [[Height (cm) / 100]²]

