13.1.5 Days of hospitalization

Days of hospitalization after treatment will be determined using the ‘Study Drug Administration’ and ‘Hospitalization Details’ eCRFs. The date and time (in format 23:59) of 1st dose of study drug and discharge will be collected.

Duration of hospitalization after treatment up through 14 days will be calculated as

- Duration of hospitalization after treatment (days) = (Date and time of discharge – Date and time of 1st dose of study drug)/60/24

Missing discharge times will be assumed to be ‘23:59’ in order to calculate the maximum duration of time hospitalized. In the event a patient is hospitalized more than 14 days, 14 days will be used for analysis.

For patients that died within the first 14 days while hospitalized, the duration of hospitalization will be imputed as 14 days in order not to underestimate the number of days of hospitalization. In the unlikely event a patient dies within 14 days but subsequent to discharge, the number of days hospitalized will be 14 minus the number of days from discharge to death.

For patients with multiple hospitalizations in the first 14 days, the sum of all intervals will be calculated for analysis.

Duration of hospitalization after treatment as a continuous variable will be summarized descriptively by treatment and analyzed using a 1-way ANOVA model with a single term for treatment.

A similar analysis will be done for the total duration of hospitalization:

- Total duration of hospitalization (days) = (Date and time of discharge – Date and time of admission)/60/24

Missing admission times will be assumed to be ‘00:00’ and missing discharge times will be assumed to be ‘23:59’ in order to calculate the maximum duration of time hospitalized.

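### The general duration formula in SAP 8.2 divides by 3660 × 24, which is not a day in any unit; neither it nor 13.1.5 states the time unit, and the two imply different ones

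*SAP*

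**What the plan says.** SAP 8.2 (Standard Calculations) sets the general rule: "Durations, expressed in days, will be calculated as follows". When both date and time are known, the difference is divided as in "Start date/time of event)/(3660x24". When a time is missing there is a fallback: "If the stop or start time is missing, only the date information will be used as follows", namely stop date minus start date plus 1.

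SAP 13.1.5 (Days of hospitalization) has its own formulas. Stay after treatment ends in "Date and time of 1st dose of study drug)/60/24", and total stay in "Date and time of admission)/60/24". Times are recorded to the minute: "The date and time (in format 23:59) of 1st dose of study drug and discharge will be collected". Stay after treatment is capped: "In the event a patient is hospitalized more than 14 days, 14 days will be used for analysis".

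Neither section names the unit of the difference. The software is fixed in section 8: "All analyses and tabulations will be performed using SAS software Version 9.4 or higher".

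**The concern.** Section 8.2 introduces its formulas as the rules by which variables will be derived, so this is operative text. The protocol (10.3.1) also leaves it to the SAP to define what counts as a day for oxygen-free days and hospital days, so the SAP is where a programmer will look.

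A wrong divisor sets two of the SAP's own requirements against each other. Section 8 has outputs checked both for accuracy and for consistency with the plan. Code that follows the plan is inaccurate, and accurate code departs from the plan; section 1 requires such departures to be documented in the study report.

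Two outputs are exposed:
- **Oxygen-free days (13.1.3)** are accumulated from dates and times, with fractional days, and the section gives no conversion formula of its own.
- **The exposure-adjusted incidence rate (11.2)** runs from the date/time of first dose to the date/time of the event in patients who have one.

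The different divisor in 13.1.5 leaves the programmer to infer one unit there and another in 8.2.

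**Working it through.** **Inputs.** Divisor in 8.2: 3660 × 24. Divisor in 13.1.5: /60/24. Cap in 13.1.5: 14 days. Units: not stated in either place.

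**1. Can the 8.2 divisor be reproduced?**
- 3660 × 24 = 87,840.
- Seconds per day: 60 × 60 × 24 = 86,400.
- Minutes per day: 60 × 24 = 1,440.
- Hours per day: 24.

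None matches. The nearest is 86,400, which differs by one digit in the first factor (3600, not 3660).

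**2. Effect of 8.2 if the difference is in seconds.** Computed days = true days × 86,400 / 87,840 = true days × 0.9836, a shortfall of 1.64%.

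| True days | 8.2 as written | Shortfall (hours) |
|---|---|---|
| 1 | 0.984 | 0.39 |
| 7 | 6.885 | 2.75 |
| 14 | 13.770 | 5.51 |
| 28 | 27.541 | 11.02 |

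With minutes the result is not close: 14 days would give 14 × 1,440 / 87,840 = 0.23. With 3600 × 24 on seconds, 1, 7, 14 and 28 days return exactly those values.

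**3. Oxygen-free days (13.1.3).** If every value goes through the date/time formula, all values are multiplied by 0.9836. The mean difference and its confidence limits shrink by 1.64% (a 1-day difference is reported as 0.984), and the ANOVA p-value does not change. That invariance fails once some records use the fallback. For an interval of exactly 7 × 24 hours, known times give 6.885, while a missing time gives 7 + 1 = 8. Of that gap of 1.115, 1 comes from inclusive date counting, which is a separate convention, and 0.115 from the wrong digit.

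**4. Exposure-adjusted rate (11.2).** For patients with the event, exposure ends at a date/time, so the 8.2 formula applies. For patients without it, exposure ends at a date, so the fallback applies and 3660 is not used. Let f be the share of true exposure that passes through the date/time formula. Leaving the plus-1 convention aside, computed exposure is true exposure × (1 − 0.0164 f). The rate is then overstated by nothing at f = 0 and by 87,840 / 86,400 − 1 = 1.67% at f = 1. The documents do not give f; it depends on how many patients have each event.

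**5. The 13.1.5 formulas.** Read left to right, /60/24 is division by 1,440, exactly the minutes in a day. A 14-day stay in minutes is 20,160, and 20,160 / 1,440 = 14.0. On seconds, the same formula would be 60 times too large (14 days gives 840), and the cap would be reached at 14 / 60 = 0.233 days, or 5.6 hours.

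**6. What 3660 does not touch.** Hospital days use the 13.1.5 formulas. Treatment duration (11.1) uses dates plus 1. The primary endpoint, any TEAE through Day 14, depends on onset day and not on a duration.

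**The case against.** The strongest case is that this is a typing slip that a competent programmer would correct without comment. Section 8 requires independent validation of all SAS programs and outputs, plus senior statistical review, to confirm that calculations are accurate. At 1.64% in both arms the effect is small. Section 13.1.3 does not cite 8.2, so its use there is an inference. A character altered in the PDF text is also possible: the Fahrenheit conversion in 11.4 appears with a digit missing, so the printed page should be checked first. All of this stands as a limit on likely impact. It does not make the rule right, and validation against the plan is weakened when the plan is wrong.

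Two stronger readings are tempting, and the documents do not support them.
- **A reader might infer that 13.1.5 is also wrong.** It is exact in minutes, and times there are collected as hours and minutes. Its defect is a missing unit label, not a wrong number.
- **A reader might infer that nearly every stay would be capped at 14 days and the comparison between arms lost.** That requires a divisor suited to minutes to be applied to seconds without anyone noticing. The total-stay formula uses the same divisor with no cap written into it, so a 14-day stay would print as 840 days and expose the mistake.

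**Conclusion.** The divisor in 8.2 is wrong as written, whatever the unit. Read as seconds, which is the evident intent, it shortens date/time durations by 1.64%, or 0.46 days over 28 days. The outputs plausibly affected are oxygen-free days and part of the exposure-adjusted rates. Where date/time and date-only records are mixed, the distortion is small but not a uniform scale factor. Hospital days, treatment duration and the primary safety endpoint are unaffected. For 13.1.5 the point is only that the unit is unstated and differs from the one implied in 8.2.

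This rests on three assumptions: that the formula is coded literally, that the difference is taken in seconds, and that 8.2 serves as the default for 13.1.3 and 11.2. The documents name SAS but do not say in what unit its date/time differences are held. The numerical effect is small, but the error sits in a governing derivation rule and should be corrected.

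**What to change.** In SAP 8.2, change 3660 to 3600 and state that the difference is in seconds. In 13.1.5, either state that the difference is in minutes and leave /60/24 as it is, or restate both formulas as seconds/(3600 × 24) so that one convention holds throughout. It would help to cite 8.2 from 13.1.3 and 11.2. Because the exposure-adjusted rate is reported in person-weeks, 11.2 should also say that days are divided by 7.

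The cost is one digit and a few short sentences in the SAP before unblinding. No data collection, sample size or analysis method changes.

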8.3 Conventions for Missing and Partial Dates

It is not expected that there will be any missing dates, however in the rare case that an AE start date or time is missing and it is unclear whether the AE is treatment emergent or not, the available information will be used to determine if an event is treatment emergent. If the classification of the event is inconclusive based on the available start/stop date information, a worst-case scenario will be taken, and AEs will be assumed to be treatment emergent.

All dates presented in the individual patient listings will be as recorded on the eCRF.

8.4 Early Discharge Assessments

If the patients are discharged from the hospital before Day 14, all the assessments planned for Day 14 should be carried out before discharge.

For all summaries and statistical analyses early discharge assessments will be analyzed and tabulated with Day 14/ EOT.

8.5 Unscheduled Visits

Only scheduled post-baseline laboratory, ECG, and vital signs values will be tabulated. Post-baseline repeat/unscheduled assessments will not be included in the summary statistics. However, these repeat/unscheduled post-baseline assessments will be listed in the relevant appendices to the CSR.

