## 8. Study Assessments and Procedures

Study procedures to assess safety, efficacy, biomarker and PK are shown in the SoA. Adherence to the trial requirements, including those specified in the SoA is essential for study conduct.

All screening evaluations must be completed and reviewed to confirm that potential patients meet all eligibility criteria within 2 weeks of clinically diagnosis of SARS-CoV-2 virus infection. The Investigator will maintain a screening log to record details of all patients screened and to confirm eligibility or record reasons for screening failure, as applicable.

Patients could be hospitalized for up to 14 days. Patients will be assessed daily while hospitalized. If the patients are discharged from the hospital before Day 14, all the assessments planned for Day 14 should be carried out before discharge. If a patient is still hospitalized after Day 14, no study drug will be administered after the last dose on Day 14.

It is preferred that the follow-up visit is in person to obtain safety laboratory tests. However, infection control or other restrictions may limit the ability of the patients to return to the clinic. In this case, the follow-up visit may be conducted by phone and only safety data will be obtained. Study drug will not be administered for early discharged patients.

To fit into the clinical practice of treating patients with severe COVID-19, screening visit and baseline visit can be combined in some patients. In that case, the number of dosing could be less than 3 times on that day. ECG, laboratory test and other test results obtained within 24 hours prior to consent can be used as baselines.

For those patients who complete the 14-day treatment period, the investigator will decide appropriate treatments for the period from Day 15 to Day 28.

A follow-up visit will be scheduled approximately on Day 28 ( $\pm 3$ ) or 14 ( $\pm 3$ ) days after the last dose for those who are discharged from the hospital before Day 14.

Procedures conducted as part of the patient's routine clinical management and obtained before signing of the Informed Consent Form (ICF) may be utilized for screening purposes, provided the procedures meet the protocol-specified criteria and are performed within the time frame defined in the Schedule of Assessments (SoA). Repeat or unscheduled tests or procedures may be performed for safety reasons or for technical issues.

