### ***Laboratory Analyses***

Laboratory data including coagulopathy panel and cardiac function panel will be summarized using summary statistics of raw data and change from Baseline values (pre-dose Day 1 values/last non-missing pre-dose value), by presenting shift tables using clinically notable ranges (Baseline to most extreme postbaseline value), and by flagging notable values in data listings. The number and percentage of patients with clinically meaningful laboratory test findings will also be summarized by treatment group and visit.

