4 OUTCOME MEASURES

Objectives	Outcome Measures
Primary	
Primary Objective: 
 • To assess the overall safety and tolerability of SIR1-365 in patients with severe COVID-19 	Primary Safety Measure: 
 • Proportion (%) of patients with any treatment-emergent adverse events (TEAEs) during the treatment period (Baseline to Day 14). Secondary Safety Measures: 
 • Proportion (%) of patients with any adverse events (AEs), serious adverse events (SAEs), and drug-related AEs during the study (Baseline to Day 14 and Day 28) • Proportion (%) of patients with clinically significant abnormality in clinical laboratory tests and electrocardiogram (ECG) during the study (Baseline to Day 14 and Day 28) • Change in parameters for coagulopathy including D-dimer, fibrinogen, coagulation tests, and platelet count during the study (Baseline to Day 14 and Day 28) • Change in parameters of cardiac function including NT-proBNP (or BNP) and high-sensitivity cardiac troponin during the study period (Baseline to Day 14 and Day 28) 
Changes in safety outcomes in patient populations with different Baseline levels of inflammatory biomarkers to assess the correlation of biomarker profile to safety outcomes.

Secondary	
Secondary Objectives: 
 1) To assess the clinical efficacy of SIR1-365 in patients with severe COVID-19 	Clinical Efficacy Endpoints: 
 • Change from Baseline to Day 7 and Day 14 in PaO₂/FiO₂ ratio

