11.3 Clinical Laboratory Evaluation

Laboratory parameters (hematology, serum chemistry, and urinalysis) will be summarized using descriptive statistics at Baseline and at each post-baseline time point by treatment group.

Changes from Baseline will also be summarized. Refer to the list of laboratory tests to be performed in [Appendix 2](#).

In addition, shift tables will be provided to assess changes in laboratory values from Baseline to the most extreme post-baseline value using clinically notable reference ranges to derive if a laboratory measurement as low, normal, or high compared to the reference ranges.

Selected laboratory parameters (refer to [Appendix 3](#)) will be graded according to NCI CTCAE v5.0¹. The number and percentage of patients with CTCAE Grade ≥ 3 laboratory values will be summarized by treatment group.

The number and percentage of patients with clinically significant laboratory test findings will also be summarized by treatment group and visit. This will be done by laboratory category and laboratory parameter, as well as by overall.

Serology test and serum pregnancy test results at screening will be listed only.

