11.5 Physical Examination

A complete physical examination will include but not limited to the evaluation of the following organs or body systems: skin; head, eyes, ears, nose, and throat; thyroid, respiratory, cardiovascular, and central nervous systems, abdomen (liver and spleen), lymph nodes, and extremities.

Abnormal findings on physical examination prior to signing of informed consent will be included in medical history CRF whereas abnormal findings started after the signing of informed consent will be included in AE CRF.

Physical examination results will be included in data listings only.

11.6 12-Lead ECG

Values for the following 12-lead ECG parameters and change from Baseline values will be summarized through descriptive statistics by treatment group and visit.

- PR interval (sec)
- RR interval (msec)
- QRS interval (msec)
- QT interval (msec)
- Corrected QT interval (msec)

Three ECGs with 1-3 min interval will be performed before 1st dose on Day 1 only, and for data recorded on continuous scale, the means of the 3 ECGs will be used as Baselines and overall interpretation will be presented as the most severe (worst case) of the respective readings for Baseline. A single ECG will be performed for all other time points.

All ECGs must be evaluated by the Investigator and assessed as normal or abnormal, including the clinical significance (Yes/No) of abnormal values. The number and percentage of patients with clinically significant abnormal interpretation of ECGs will also be summarized by treatment group and visit.

The maximum increase in corrected QT interval from Baseline will be summarized through descriptive statistics by treatment group.

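### SAP 8.5 keeps repeat and unscheduled laboratory, ECG and vital-sign values out of every table, so worst-value and any-time safety results can only be unchanged or understated in each arm

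*SAP*

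**What the plan says.** SAP 8.5 (Unscheduled Visits) sets a general rule: "Only scheduled post-baseline laboratory, ECG, and vital signs values will be tabulated". It adds: "Post-baseline repeat/unscheduled assessments will not be included in the summary statistics". The excluded values go to listings: "However, these repeat/unscheduled post-baseline assessments will be listed in the relevant appendices to the CSR".

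Several later outputs describe a worst value or an any-time event:

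- SAP 11.3: "shift tables will be provided to assess changes in laboratory values from Baseline to the most extreme post-baseline value", the number with CTCAE Grade ≥3 values, and clinically significant findings by visit and overall.
- SAP 11.4: vital-sign abnormality rates by treatment group, as well as by visit.
- SAP 11.6: "The maximum increase in corrected QT interval from Baseline will be summarized".
- SAP 4, a secondary safety measure: "Proportion (%) of patients with clinically significant abnormality in clinical laboratory tests and electrocardiogram (ECG) during the study", to Day 14 and to Day 28.

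Protocol section 8 foresees off-schedule tests: "Repeat or unscheduled tests or procedures may be performed for safety reasons or for technical issues". Protocol 8.2.5 lets the investigator repeat a clinically significant abnormal ECG. SAP 15 states that no protocol-specified analysis has changed.

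**The concern.** Leaving unscheduled values out of by-visit means is ordinary practice, because it keeps each visit's summary comparable. The same filter does not suit a maximum, a most-extreme shift or an any-time count, where the question is whether the patient ever reached a given level.

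At least some of the excluded tests are done because of a safety concern, so they are more likely than scheduled ones to show an abnormality. An ECG taken on Day 4 for palpitations, for example, would not enter the maximum QTc increase.

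Safety is the primary objective, there are about 30 patients per arm, and a single case can matter to the reading of a table. A reader who sees a table of most extreme values will assume it covers everything recorded.

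**Working it through.** The documents give no figure on this point, so there is none to reproduce. The check compares the texts, counts from the Schedule of Assessments, and adds an illustration on assumed inputs.

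**1. Does any later section restore the excluded values?** No. SAP 11.3, 11.4 and 11.6 do not say that unscheduled values count, so a programmer following 8.5 would filter them out. Protocol 10.3.2 specifies both the shift to the most extreme value after baseline (including the coagulation and cardiac panels) and the maximum QTc increase, and limits neither to scheduled tests. The restriction is therefore a narrowing that SAP 15 does not declare.

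**2. Direction within an arm.** Let S be a patient's scheduled post-baseline values and A all recorded ones, with S contained in A. Then max(S) ≤ max(A) and min(S) ≥ min(A). A patient who meets a threshold in S also meets it in A. With the denominator held fixed, the scheduled-only count or maximum is equal to, or less extreme than, the one based on all values.

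**3. Scheduled post-baseline opportunities per patient.**

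| Assessment | Scheduled post-baseline days | Maximum number |
|---|---|---|
| ECG | 7, 10, 14/EOT, follow-up | 4 |
| Coagulation and cardiac panels | 3, 7, 10, 14/EOT, follow-up | 5 |
| Routine laboratory tests | 2 to 14 daily in hospital, follow-up | 13 + 1 = 14 |

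Vital signs are also scheduled daily in hospital to Day 14. A patient discharged on Day 5 has two scheduled post-baseline ECGs (the discharge assessment, tabulated as Day 14/EOT under SAP 8.4, and follow-up), or one if follow-up is by phone.

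**4. Gap after treatment.** Day 14 ± 2 ends at Day 16, and Day 28 ± 3 starts at Day 25. For a patient treated in hospital to Day 14, the schedule lists no test on Days 17 to 24 (8 days) under any visit window.

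**5. Weight of one patient.** 1/30 = 3.3 percentage points of an arm's rate.

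**6. Illustration; both inputs are assumptions.** Let p be the true any-time incidence and s the share of affected patients whose qualifying value appears only at an unscheduled test. The tabulated incidence is q = p(1 − s), and the chance that an arm of 30 shows at least one case is 1 − (1 − q)^30.

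| p | s | q | Chance of ≥1 case, all values | Chance of ≥1 case, scheduled only |
|---|---|---|---|---|
| 5% | 10% | 4.5% | 78.5% | 74.9% |
| 5% | 25% | 3.8% | 78.5% | 68.2% |
| 5% | 50% | 2.5% | 78.5% | 53.2% |
| 10% | 10% | 9.0% | 95.8% | 94.1% |
| 10% | 25% | 7.5% | 95.8% | 90.4% |
| 10% | 50% | 5.0% | 95.8% | 78.5% |
| 20% | 10% | 18.0% | 99.9% | 99.7% |
| 20% | 25% | 15.0% | 99.9% | 99.2% |
| 20% | 50% | 10.0% | 99.9% | 95.8% |

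The loss is small when few cases depend on unscheduled tests, and material for uncommon events when many do. The documents do not say which applies.

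**The case against.** The best defence is that scheduled-only tables give both arms the same planned opportunities to show an abnormality. Off-schedule data are also recorded selectively: under Protocol 8.2.4, results of local tests outside the protocol must enter the eCRF only if they change management or are clinically significant. This stands as a reason to keep a scheduled-only version alongside, but not as a reason to present it as the worst value.

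The second defence is that the cases appear elsewhere. Protocol 8.2.4 and Appendix 4 make clinically significant laboratory, ECG and vital-sign findings adverse events. SAP 11.2 tabulates these by preferred term, grade and onset, with a separate table for ALT, AST and creatinine. This also stands, and it limits the harm. It does not correct the worst-value tables or the separate secondary measure.

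Third, the by-visit layout of the ECG abnormality table comes from Protocol 10.3.2, not from 8.5. That is right, and it means that changing 8.5 alone would not produce an any-time ECG rate.

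A reader might infer more than the documents support:

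- *That 23 of the 27 days from Day 2 to Day 28 are lost for ECGs and 22 of 27 for the panels, or that no laboratory test is scheduled on Days 15 to 27.* The day counts are nominal (27 − 4 and 27 − 5), include days after discharge, and count calendar days rather than excluded values. The Days 15 to 27 statement is wrong: the windows reach Days 15–16 and 25–27, and follow-up for patients discharged early is 14 ± 3 days after the last dose.
- *That every excluded value was selected for being abnormal.* The protocol also allows repeats for technical issues.
- *That SAP 8.5 and 11.3 contradict each other outright.* The most extreme scheduled value is a coherent quantity. The fault is an unstated narrowing.
- *That the comparison is tilted toward the drug.* The rule applies to both blinded arms, and nothing in the documents gives a between-arm difference.

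**Conclusion.** The point holds for worst-value and any-time outputs only. As written, SAP 8.5 leaves each arm's most-extreme shifts, Grade ≥3 count, overall abnormality rates and maximum QTc increase unchanged or understated, and departs from Protocol 10.3.2 without saying so.

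The effect is likely to be largest for QTc and for the coagulation and cardiac panels. It should be smaller for routine laboratory tests and vital signs, which are scheduled daily in hospital to Day 14. Each omitted patient costs about 3.3 points. The total size and any between-arm bias cannot be calculated.

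The direction rests on two conditions: a fixed denominator, and a comparison with all recorded values. A scheduled value later found technically invalid is a separate matter. The excluded values remain in listings, and the primary endpoint (any TEAE to Day 14) is not directly affected, so this is a correction the plan should make rather than a threat to the main result.

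**What to change.** Amend SAP 8.5 before unblinding; SAP 8 treats unspecified analyses added after that as post hoc.

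- By-visit descriptive summaries: scheduled values only, as now.
- Most-extreme shifts, CTCAE Grade ≥3, overall clinically significant laboratory and ECG abnormality, overall vital-sign abnormality, and maximum QTc increase: all valid post-baseline values, scheduled or not, within the Day 14 and Day 28 windows. Exclude technically invalid results. State how a follow-up visit on Days 29 to 31 counts, since Day 28 + 3 = 31.
- Add an overall any-time ECG row, because Table 14.3.8.2 is by visit only.
- Keep the scheduled-only version as a supporting table, and report the number of unscheduled tests per arm.

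The cost is a short SAP amendment, a changed program filter and one extra table row, using values that 8.5 already sends to listings. The downside is that the number of off-schedule tests may differ by arm and some of those results are recorded selectively. The supporting table and the test counts make that visible. If the sponsor prefers the present rule, SAP 15 should declare it and the table titles should say scheduled values only.
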